Frequency of implant passing incidents found to be associated with an Adverse Event will be reported. Failure in this endpoint is defined, on a per patient basis, as the presence of a spontaneous implant passing event (one or more clips being passed) determined by a blinded study investigator to be associated with an Adverse Event (AE), where "Associated" is defined as a device-related AE that is temporally related to the implant passing event. See Section 9.4.2 for a detailed description of investigator determination of Adverse Event relatedness to implant passing events.

Frequency of implant passing (either clips or sutures) will be explicitly collected at each followup visit; however, events may be reported between visits or during unexpected visits. When implant passing is reported, subjects will be asked to collect and provide passed implants, and an in-person evaluation will be performed, involving a visual cuff closure and healing assessment.

(5) Comparison of Incidence of adverse events

The number of adverse events and serious adverse events, as well as the proportion of subjects with adverse events, will be summarized by treatment arm, severity, and relatedness to device. Adverse events will be coded using the validated MedDRA system. By-subject listings will be provided for all safety data. Incidence of adverse events will then be compared using Fisher's

Exact test to assess possible significance or relationship of cuff closure device to adverse event rate.

(6) Comparison of change in dyspareunia

Dyspareunia will be pre-operatively baselined and assessed at each follow-up timepoint, including any unexpected visits, using the sexual pain and discomfort domain (four questions) from the validated Female Sexual Function Index (FSFI).^{21,22} Individual success is defined as non-increase in dyspareunia from baseline to six months. Fisher's Exact Test will be used to compare this measure between test and reference groups.

(7) Comparison of change in pain

Patient pain will be pre-operatively baselined and assessed at each follow-up timepoint, including any unexpected visits, using a validated 11-point numerical rating scale²³ (no pain: 0 – the most pain: 10). Individual success is defined as non-increase in pain between baseline and six months. Fisher's Exact Test will be used to compare this measure between test and reference groups.

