Secondary Endpoint (3) Comparison of implant passing rates.

Data collection: Implant passing rates will be calculated and the percentage of subjects experiencing one or more implant passing events will be compared between the test and control groups at six weeks and at six months.

Acceptance Criteria: Endpoint success is defined as a percentage of subjects experiencing implant passing in the test group less than or equal to that of the reference group.

Statistical Analysis Method: A two-sided Fisher's Exact Test will compare (test versus reference) percentage of subjects experiencing implant passing events between test and reference groups. Assessment of this is independent of the primary study endpoints.

Secondary Endpoint (4) Relationship of Implant passing to Adverse Events.

Data collection: Frequency of implant passing events associated with an Adverse Event will be evaluated through six-weeks post-operative. Associating implant passing to an Adverse Event will include consideration of temporal and possible causal relationship. The AE relatedness terms described in Section 8.3.3 will be utilized in determination of implant passing to a given Adverse Event, where "relatedness to study intervention" is replaced with "relatedness to implant passage." This will not replace determination of relatedness to the study device, which will be performed separately according to study safety reporting details. Adverse Events determined to be 'probably' or 'definitely' related to an implant passing event will be considered a per patient failure of the primary efficacy endpoint. Relationship of implant passing events to AEs will be reported independently and compared between test and control groups.

Acceptance Criteria: Endpoint success is defined as a percentage of subjects experiencing implant passing event related to an AE in the test group less than or equal to that of the reference group.

Statistical Analysis Method: A two-sided Fisher's Exact Test will compare (test versus reference) percentage of subjects experiencing implant passing event associated with an AE between test and reference groups. Assessment of this is independent of the primary study endpoints.

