10.2 ABBREVIATIONS AND DEFINITIONS

Adverse Events (AE)

For the purpose of this clinical investigation plan, an adverse event (AE) is any untoward medical occurrence, unintended disease or injury or any untoward clinical signs in subjects whether or not related to the Investigational Product and includes events related to the procedures involved (any procedure in the clinical investigation plan). All Adverse Events (including serious Adverse Events) will be classified by outcome, severity, treatment taken, and attribution to study intervention. See Section 8.3 for more details.

Associated Adverse Event

Defined as an AE that is both device-related (to either clip or reference device in accordance with Section 8.3.3) and that is temporally related to the implant passing event.

Body Mass Index (BMI)

Code of Federal Regulations (CFR)

Vaginal Cuff Dehiscence

Vaginal cuff dehiscence has a reported incidence of up to one in twenty (5%) among patients undergoing laparoscopy^{5–7} even with robotic assistance.⁸ Vaginal cuff dehiscence has been defined in this study as a rupture of the surgical wound requiring surgical re-intervention. Small openings in approximated vaginal mucosa that resolve without intervention will be recorded as part of cuff closure and healing characterization endpoints, but will not be deemed as failures, since intervention was not required to bring about recovery

Food & Drug Administration (FDA)
Good Clinical Practice (GCP)
Informed Consent Form (ICF)
Institutional Review Board (IRB)
Instructions For Use (IFU)
Investigational Device Exemption (IDE)

Laparoscopic Assisted Vaginal Hysterectomy (LAVH)

LAVH is the surgical excision of a women's uterus using a combination of vaginal and laparoscopic approaches LAVH typically includes laparoscopically detaching the uterine body from the surrounding upper supporting structures. The vaginal apex is entered using a vaginal approach, and the cervix and uterus are detached from the remaining supporting structures. The uterus is then removed through the vagina.

Poly-p-dioxanone (PDO)

A biologically inert, bio-absorbable polymer that degrades naturally by hydrolysis. Both traditional suture and Zip-stitch[™] clips are composed of this material.

Principal Investigator (PI)

Serious Adverse Events (SAE)

Serious AEs are a subset of AEs. An SAE is one that:

- Results in death
- Results in life-threatening illness or injury
- Results in a permanent impairment of a body structure or function

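### Secondary endpoint 4 (implant passing linked to an adverse event) carries two association rules, a misplaced failure label and a clips-only parenthesis that need reconciling before unblinding

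*Combined protocol and SAP*

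**What the plan says.** **Association, first rule.** Protocol Section 3.2(4) says that association "is defined as a device-related AE that is temporally related to the implant passing event". The glossary in Section 10.2 gives the same two conditions and covers both arms: "Defined as an AE that is both device-related (to either clip or reference device in accordance with Section 8.3.3". Neither place says which of the five relatedness grades in Section 8.3.3 makes an AE device-related.

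**Association, second rule.** Section 9.4.4 applies the Section 8.3.3 grades to the passing event in place of the study intervention. It singles out "Adverse Events determined to be 'probably' or 'definitely' related to an implant passing event" and adds: "This will not replace determination of relatedness to the study device, which will be performed separately".

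**Failure label.** Section 9.4.4 then says that AEs so "related to an implant passing event will be considered a per patient failure of the primary efficacy endpoint". Section 3.1 defines a primary failure as any spontaneous passing event, with no AE condition.

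**Which implants count.** The failure definition in Section 3.2(4) reads "one or more clips being passed) determined by a blinded study investigator to be associated with an Adverse Event". The next paragraph of the same endpoint collects passing of clips and of sutures, and Section 3.1 counts both.

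**How it is judged.** The synopsis and Section 3.2(4) only report the frequency. Section 9.4.4 adds a two-sided Fisher's exact test between arms and an acceptance criterion: a percentage of subjects with passing "related to an AE in the test group less than or equal to that of the reference group".

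**Cross-reference.** Section 3.2(4) directs: "See Section 9.4.2 for a detailed description of investigator determination of Adverse Event relatedness to implant passing events". Section 9.4.2 mentions the assessment briefly and names endpoint 4, but the rule itself is in Section 9.4.4.

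**The concern.** A programmer or adjudicator following Section 3.2 and one following Section 9.4.4 would build different event lists for the same endpoint. Events should be rare and the arms are small, so one woman classified differently can decide the acceptance criterion. If the choice is left open, it could be made after treatment codes are known, because Section 6.3 places unblinding after the last six-week visit.

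The clips-only parenthesis raises a second problem. The criterion compares test with reference. If only clips count, women closed with suture have nothing to contribute, and the test arm is judged against a rate held at or near zero by definition.

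**Working it through.** **1. The two rules side by side.**

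| Case | Sections 3.2(4) and 10.2 | Section 9.4.4 |
|---|---|---|
| Device-related AE, close in time to passing, graded only potentially related to the passing | counts | does not count |
| AE graded probably related to the passing, judged not device-related | does not count | counts |
| Device-related AE, close in time, graded probably or definitely related to the passing | counts | counts |

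Neither set contains the other. The documents give no expected distribution of grades, so the number of women affected cannot be estimated.

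**2. Effect of the misplaced label on the primary endpoint.** An AE related to a passing event presupposes a passing event. Under Section 3.1 that woman is already a primary failure, so the primary count does not change. The label does leave Section 9.4.4 without an explicit per-patient failure rule for endpoint 4.

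**3. Sample size (the plan's own figure).** 35 / (1 − 0.10) = 38.9, rounded up to 39 test; 39 / 2 = 19.5, rounded up to 20 reference; total 59. This matches the synopsis and Section 4.1.

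**4. Effect of a literal clips-only reading.** The documents give no rate of AE-associated passing. I assume a true per-subject rate p, equal in both arms, from 1% to 10%.

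- Clips only, with the reference at 0/20: the criterion is met only with 0/39 test events, so P = (1 − p)^39.
- Both implants counted: with y reference events the criterion allows up to floor(39y/20) test events, so P = Σ Pr(Y = y) × Pr(X ≤ floor(39y/20)), with X ~ Bin(39, p) and Y ~ Bin(20, p).

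Example at p = 2%. Clips only: 0.98^39 = 0.455. Both counted:

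- y = 0: 0.6676 × 0.4548 = 0.304
- y = 1: 0.2725 × 0.8168 = 0.223
- y = 2: 0.0528 × 0.9925 = 0.052
- y ≥ 3: about 0.007
- Sum: 0.586

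| Assumed rate, both arms | Both implants counted | Clips only |
|---|---|---|
| 1% | 72.5% | 67.6% |
| 2% | 58.6% | 45.5% |
| 5% | 44.3% | 13.5% |
| 10% | 43.6% | 1.6% |

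With 35 versus 18, closer to the evaluable target, the pairs are 74.5% and 70.3%, 60.8% and 49.3%, 45.4% and 16.6%, and 43.4% and 2.5%.

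**5. Sensitivity to one woman.** With no reference events, a single test event (1/39 = 2.6% versus 0/20) fails the criterion, while Fisher's test gives p = 1.0. Against 0/20, Fisher's test first falls below 0.05 at 8/39 (p = 0.042).

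**The case against.** The strongest reply is that the parenthesis is a drafting slip which the rest of the protocol corrects. Section 3.1, the next paragraph of Section 3.2(4) and the glossary all include sutures or the reference device. Section 9.4.4, where the comparison is specified, has no clips-only limit and presupposes reference events. That reply stands. A reader might infer that the suture arm cannot have an event, but the documents do not support it. Even on the literal wording, a woman randomized to suture and closed with clips as the alternate method (Section 6.5.1) would be analysed in the reference arm under ITT and could have an event.

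A reader might also infer that the stray label alters the primary endpoint or moves events out of endpoint 4. Section 9.4.4 does not say that these cases count for the primary endpoint instead of endpoint 4, and it keeps a separate criterion for endpoint 4. The summary of changes records that the reference to associated safety and healing events was removed from the primary endpoint, so the sentence looks like residue.

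It can further be said that the probably/definitely threshold is attached, by its own words, to the primary endpoint, and that for endpoint 4 Section 9.4.4 asks only for temporal and possible causal consideration, which overlaps with Section 3.2. This softens the conflict but does not remove it. On that reading Section 9.4.4 gives endpoint 4 no threshold at all, and it still grades relatedness to the passing where Sections 3.2 and 10.2 use relatedness to the device.

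Finally, the synopsis labels the secondary endpoints exploratory, and Sections 4.2 and 9.2 say they are unpowered. That limits the consequence. It does not tell anyone which rule to apply, and Section 9.4.4 still sets a pass/fail criterion.

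**Conclusion.** The inconsistency is real and sits in current text. Endpoint 4 has two association rules that can classify the same woman differently, a failure label pointing to the wrong endpoint, a parenthesis at odds with four other places, an imprecise cross-reference, and an unresolved choice between reporting and comparing. It should be corrected, but its weight is modest: the endpoint is exploratory and unpowered, and no primary count is affected.

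The conflict between the rules cannot be sized from the documents. The figures above measure only the literal clips-only reading. They rest on an assumed event rate, equal in both arms, and on a reference arm with no events. The loss in the chance of meeting the criterion runs from about 5 percentage points at 1% to 42 at 10%. That bias is against the test device, so the wording creates no favourable claim.

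**What to change.** Fix these before the six-week unblinding:

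1. **Section 3.2(4):** change the parenthesis to 'one or more clips or sutures being passed'.
2. **Section 9.4.4:** relabel the per-patient failure as a failure of secondary endpoint 4.
3. **Sections 3.2, 9.4.4 and 10.2:** use a single association rule. The Section 9.4.4 rule (AE graded probably or definitely related to the passing event) is a natural choice because it is the only one with a stated threshold. If the device-related rule is kept instead, state the grade it requires. Step 2 alone would attach the Section 9.4.4 threshold to endpoint 4 and leave it in conflict with Sections 3.2 and 10.2, so steps 2 and 3 belong together.
4. **Section 3.2(4):** point the cross-reference to Section 9.4.4.
5. **Synopsis, Sections 3.2 and 9.4.4:** state alike whether the endpoint is comparative or report-only.

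The cost is wording in a few places. Section 9.4.4 already calls for separate grading of relatedness to the passing and to the device, so no new assessment, visit or subject is needed.

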12-months long. Consequently, this study is expected to take a total of 15 to 17 months from beginning of enrollment to completion of follow-up. Additionally, study blinding will be removed after the last subject completes their six-week follow-up timepoint, and 6 and 12-month follow-up will be collected unblinded. Data will be submitted for regulatory

study follow-up after 6 and 12 months.

Participant Duration: Intervention will occur at the time of surgery and subjects will complete a

12-month follow-up program, including in-person visits at one week, six weeks, and six months, as well as a telephone follow-up at 12-months.

review following unblinding at six weeks, and again after completion of

Statistical Methods: Analysis Populations:

Intent-to-treat population (ITT): This population will include all subjects enrolled and randomized to test or reference treatment. Subjects will be analyzed according to the treatment to which they were randomized,

regardless of the treatment they actually received.

Safety population: This population will include all subjects enrolled and randomized to test or reference treatment. Subjects will be analyzed according to the treatment that they received; patients randomized to the reference arm that receive Zip-stitch™ will be included in the Zip-stitch™ safety population. Similarly, patients randomized to the Zip-stitch™ arm that receive sutures will be included in the reference safety population.

Primary and secondary efficacy endpoint analyses will be performed on the ITT population. All safety analyses will be performed on the Safety population.

Efficacy Analysis:

Unless otherwise stated the analyses of efficacy endpoints will be based on the ITT population as follows.

One-sided endpoint analyses will be performed with 80% statistical power; corresponding *p*-values will be reported, and all two-sided analyses and comparisons between groups will be performed assuming a 0.05 significance level. The corresponding *p*-values and 95% confidence intervals (CIs) will be reported.

Primary Efficacy Endpoint:

Frequency of spontaneous implant passing events will be reported through six weeks. Event frequency will be numerically compared to a performance target of 5%.

Secondary Efficacy Endpoints:

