Study recruitment is designed to avoid any potential coercion. Potential subjects will have decided with their doctor to undergo minimally invasive hysterectomy prior to discussing possible participation in this trial. Once a potential candidate has been successfully pre-screened, the informed consent process will be conducted by a study investigator or coordinator other than the potential subject's doctor.

Study enrollment takes place during surgery. Intra-operative enrollment criteria are designed to specifically evaluate closure of the vaginal cuff during laparoscopic hysterectomy, the step Zip-stitch™ is designed for. Subjects who may have unforeseen complications during the anesthesia or colpotomy process for example, are not intended for treatment and their procedure should continue according to standard of care.

Study randomization will take place via blinded, variable block size randomization envelopes stratified by site. Subjects will be blinded to the treatment they receive, but as the operating surgeon cannot be blinded to the treatment provided, this study cannot be fully double-blinded. Every effort will be made to minimize opportunities for unblinding during post-operative data collection. In particular data collection will be performed by a different investigator surgeon without access to the blinded to treatment assignment, including through the electronic data capture system.

Data unblinding will take place after completion of six-week follow-up. This enables reporting of the primary study endpoints and most secondary study endpoints. The data collected at the 6 and 12-month follow-up visit and telephone call are limited to dehiscence, pain, dyspareunia, and adverse events. Adverse events are likely to have significant clinical sequelae, and therefore not likely to be forgotten. Pain and dyspareunia are evaluated based on experience in the time frame of the call, and therefore are not affected by recall bias. No statistical comparisons are being made using 12-month data.

Protocol QD-PRO-045 Rev 005

Some secondary endpoints evaluate incidence and rate of various events; others compare test and reference groups. Comparisons will be made using two-sided Fisher's Exact Tests. Secondary endpoints are not powered to reach statistical significance but are intended to provide additional information and indicate possible safety and efficacy trends.

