9.2 SAMPLE SIZE DETERMINATION

The study size was based on FDA's recommendation of the sufficient sample size to support a future 510(k) notification.

A minimum of 30 and a maximum of 40 subjects in the test group have been requested for this study. Assuming a 10% loss to follow-up, a goal of 39 (maximum of 44) subjects are expected to be enrolled in the test group, and a goal of 20 (maximum of 22) are expected to be enrolled in the reference group, for a total goal of 59 (maximum of 66).

No statistical assessment of the rate of successful cuff closure is required for analysis of the primary study endpoints. The rate of implant passing events on a per-patient basis will be numerically compared to the 5% performance target. Nonetheless, the 95% confidence interval will be reported for this endpoint.

This study is also not powered to address secondary endpoints. It is not expected that statistical analyses will yield conclusive results on exploratory endpoints.

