9.4.5 ANALYSIS OF SECONDARY SAFETY ENDPOINTS

The Safety population will be the analysis population for all safety analyses.

Secondary Endpoint (5) Comparison of incidence of adverse events.

Data collection: Adverse Events will be tabulated for both the test and reference groups. All AEs and SAEs will be MedDRA-coded and summarized by treatment arm. In addition, the number and proportion of AEs and SAEs will be calculated for each group. For each MedDRA-coded medical term, the proportion of subjects who experience at least one of the following will be reported and compared.

Adverse event

- Adverse event related to treatment
- Serious adverse event
- Serious adverse event related to treatment
- Adverse event leading to study discontinuation
- Serious adverse event leading to study discontinuation

Classification of AEs will also be presented and compared. Events will be reported by MedDRA system organ class and preferred term. Adverse Events will be compared by severity and device relatedness between the test and reference groups.

Acceptance Criteria: There is no defined endpoint acceptance criteria for the comparison of adverse events.

Statistical Analysis Method: A two-sided Fisher's Exact Test will compare (test versus reference) rate of incidence of adverse events by six months post-operative. Assessment of this is independent of the primary study endpoints.

Secondary Endpoint (6) Comparison (test to reference group) of non-increase in subject dyspareunia scores from baseline to 6-months post-operative.

Data collection: Individual subject dyspareunia will be assessed using the relevant sexual discomfort module of the validated Female Sexual Function Index (FSFI). Higher scores indicate good sexual function with little or no sexual discomfort, and lower scores indicate poor sexual function with higher levels of sexual discomfort. Scores of zero indicate no sexual activity and will not be included in comparison of non-increase in dyspareunia.

Acceptance Criteria: A subject level failure is defined as a decrease in sexual function score (signifying an increase in dyspareunia). Endpoint success is defined as the same or lower rate of FSFI score decrease in the test group at six months when compared to the reference group at six months.

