Statistical Analysis Method: Comparison (test versus reference group) of failure rates from baseline to six-month follow-up will be made using a two-sided Fisher's Exact Test. Assessment of this is independent of the primary study endpoints.

Secondary Endpoint (7) Comparison (test to reference group) of non-increase in subject pain scores from baseline to 6-months post-operative.

Data collection: Individual subject pain will assed using a validated 11-point numerical pain rating scale, where "0" corresponds to no pain and "10" corresponds to the most pain possible. Pain score will be collected at all study timepoints and unexpected visits; however, statistical assessment will be performed between baseline and six-month score.

Acceptance Criteria: A subject level failure is defined as an increase in reported subject pain score. Endpoint success is defined as the same or lower rate of increase in reported pain in the test group at six months when compared to the reference group at six months.

Statistical Analysis Method: Comparison (test versus reference group) of failure rates from baseline to six-month follow-up will be made using a two-sided Fisher's Exact Test. Assessment of this is independent of the primary study endpoints.

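### Pain and dyspareunia are compared between arms only as a yes/no non-increase; a supportive baseline-adjusted score difference should be added beside that comparison

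*Combined protocol and SAP*

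**What the plan says.** Section 3.2 defines individual success for pain (endpoint 7) and dyspareunia (endpoint 6) in parallel terms: "Individual success is defined as non-increase in pain between baseline and six months" and "Individual success is defined as non-increase in dyspareunia from baseline to six months". Section 9.4.5 restates this as failure. For pain: "A subject level failure is defined as an increase in reported subject pain score". For dyspareunia, failure is a fall in the FSFI pain-domain score, where lower means more discomfort.

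The test is the same for both: "Comparison (test versus reference group) of failure rates from baseline to six-month follow-up will be made using a two-sided Fisher's Exact Test". The synopsis sets the level: "all two-sided analyses and comparisons between groups will be performed assuming a 0.05 significance level". Each endpoint also has a numerical acceptance criterion, met when the failure rate in the test arm is no higher than in the reference arm.

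Pain is scored 0 to 10 and dyspareunia by the FSFI domain, both at baseline and at each follow-up. Section 9.4.5 leaves FSFI scores of zero (no sexual activity) out of the dyspareunia comparison. Beyond the responder comparison, the plan offers only general descriptive summaries (Section 9.4.1) and individual listings (Section 9.4.9).

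On purpose and power, Section 9.2 says: "This study is also not powered to address secondary endpoints". Section 4.2 says: "Secondary endpoints are not powered to reach statistical significance but are intended to provide additional information and indicate possible safety and efficacy trends".

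**The concern.** Two graded scores, each measured before and after surgery, are reduced to whether the woman ended worse than she started. A woman whose pain falls by 6 points counts the same as one whose pain falls by 1. A device that blunts recovery without pushing women above their own baseline barely registers. The outcome also depends on where a woman starts: at pain 0 she can only stay or fail, and at 10 she cannot fail.

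At stake is how well the trial can show a trend in patient-reported harm. Section 2.3.2 records a theory that the clips may contribute to dyspareunia while they degrade, and the synopsis puts absorption at five to eight months, so six months is a relevant time. The synopsis promises 95% CIs with its comparisons, but for these endpoints they would describe failure proportions. Nothing in the plan says by how many points the arms differ.

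**Working it through.** **Sample size.** Section 4.1 aims for 35 test subjects with 10% loss. 35/0.9 = 38.9, rounded up to 39; 39/2 = 19.5, rounded up to 20; total 59, as stated. About 20 × 0.9 = 18 reference women would be evaluable, so pain is compared in roughly 35 v 18. The documents state no power for endpoints 6 and 7.

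**Assumed inputs.** The documents give no SD, correlation, expected change or important difference. The main case assumes SD 2.5, baseline-to-six-month correlation ρ = 0.5, baseline mean 5 and a fall of 2 in the reference arm. Scores are rounded and truncated to 0–10.

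**Hand check for a uniform shift.**
- SD of change = 2.5 × √(2 × (1 − 0.5)) = 2.5. After rounding, an increase means a change above about 0.5. Reference failure rate ≈ Φ(−(0.5 + 2)/2.5) = Φ(−1.0) = 16%. With a 1.5-point shift the test-arm rate is Φ(−0.4) = 34%; with 2 points, Φ(−0.2) = 42%. Fisher must separate 34% or 42% from 16% in 35 v 18 women.
- ANCOVA residual SD = 2.5 × √(1 − 0.25) = 2.17. SE = 2.17 × √(1/35 + 1/18) = 2.17 × 0.290 = 0.63. The 95% CI would be about ± 2.01 × 0.63 = ± 1.3 points. Approximate power is Φ(1.5/0.63 − 2.01) ≈ 64% at 1.5 points and Φ(2/0.63 − 2.01) ≈ 88% at 2, before the loss from truncation.

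**Simulated power, uniform shift, two-sided 0.05.**

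| Baseline mean, fall, difference | Fisher on non-increase | ANCOVA |
|---|---|---|
| 5, 2, 1.5 | 21% | 62% |
| 5, 2, 2 | 39% | 85% |
| 4, 1, 1.5 | 28% | 61% |

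Over ρ = 0.3 to 0.7 with falling scores (means 4 to 2, or 3 to 1), power at 2 points is 32–57% for Fisher and 74–94% for ANCOVA. With no mean fall (4 to 4) it is 44–77% and 79–95%. Type I error is about 2–4% for Fisher and about 5% for ANCOVA.

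**Large-sample check.** For normal scores with a mean shift, the information the cut keeps relative to ANCOVA is φ(z_p)²/[p(1 − p)] × (1 + ρ)/2, where p is the proportion who increase. At ρ = 0.5 and p = 0.2: 0.280²/0.16 × 0.75 = 0.37. At p = 0.5 it is 0.48, and at p = 0.05 it is 0.17.

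**Harm in a subset.** Here a share of test women end at least 1 point above baseline and the rest follow the reference course (35 v 18, SD 2.5, ρ = 0.5). Ranges show separate simulation runs.

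| Scenario | Fisher | ANCOVA |
|---|---|---|
| Baseline 5, fall 2, 30% harmed | 34–35% | 26–28% |
| Baseline 5, fall 2, 40% harmed | 57–60% | 45–46% |
| Baseline 4, fall 4, 30% harmed | 72% | 52% |
| Baseline 5, fall 2, 30% harmed by 4 points | 34% | 50% |

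Neither analysis is better in every case.

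**Dyspareunia.** Dropping zero scores leaves fewer than 35 v 18; how many fewer is not stated. If 24 v 12 or 18 v 9 remained (assumed), power for a 2-point shift on the 0–10 model (means 4 to 2, ρ = 0.5) would be 28% v 66% or 18% v 53%, Fisher first. The 0–10 scale is only a stand-in for the FSFI domain.

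**The case against.** The plan labels these endpoints exploratory, disclaims power for them and does not expect conclusive results. The scores stay visible in summaries and listings. Non-increase also asks a legitimate question of its own: whether individual women end up worse. Local clip problems in a few women are at least as plausible as a shift in everyone, and for mild harm in a subset the responder test does better. All of this stands, and it is why the responder comparison should remain.

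What it does not answer is the missing estimate. An endpoint meant to indicate trends is better served by a difference in points with its interval alongside the responder table.

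A reader might go further and infer that the cut discards most of the information whatever the pattern of harm, so that ANCOVA should become the main comparison. That holds across most of the assumed range for a mean shift, but not for mild subset harm. Demotion would also detach the acceptance criterion, which is written on failure rates, from the main analysis.

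A reader might also infer that nearly every woman must be a success. The documents do not support that. An expected improvement is stated only for dyspareunia (Section 2.3.2). For pain, Section 2.3.4 reports a decrease during the earlier study's extension period, not an expected fall from pre-operative baseline. In the pain scenarios above with falls of 2 and 1, about 16% and 27% of reference women fail.

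**Conclusion.** The point holds as a gap in exploratory secondary endpoints: scores are collected at both times, and no between-arm estimate on their scale is planned. For a uniform shift in pain, the responder test alone has roughly a third to a half of the power of the adjusted score analysis (21/62 = 0.34; 39/85 = 0.46). For slight worsening in a subset the responder test is the more sensitive, so the two complement each other.

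The power figures rest on assumed SD, correlation, baseline and fall. The 1.5-point case with a fall of 2 represents less improvement rather than average worsening (−2 + 1.5 = −0.5), and the documents give no clinically important difference. The dyspareunia figures are illustrative only. This is neither a sample-size error nor a flaw in the primary analysis, and no primary conclusion changes.

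**What to change.** In Section 9.4.5, endpoints (6) and (7), keep the non-increase comparison, its Fisher's exact test and its acceptance criterion. Add to each a pre-specified supportive ANCOVA of the six-month score on arm, baseline score and site (randomisation is stratified by site), reporting the adjusted difference with its 95% CI. State the direction of benefit, since higher is worse for pain and better for the FSFI domain.

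For dyspareunia, restrict the model to women with non-zero scores at both baseline and six months, in line with the existing exclusion, and report the number analysed in each arm. Otherwise inactivity would be read as the worst discomfort. The model does not recover the excluded women, and the Section 4.2 caution about using only part of the FSFI still applies.

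Add a rank-based check, because scores may pile up at the end of the scale that means no pain or discomfort.

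The cost is a few lines of text and one extra model per endpoint, plus the check. No new data are needed, and the endpoint definitions in the synopsis and Section 3.2 can stay as they are.
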